12.6.3 Safety Evaluation

As this study is observational by design and is conducted in a post-market setting, adverse event (AE) reporting will follow the Sponsor's already established post-market Safety Surveillance Procedures for spontaneously-reported events. All study personnel and study participants will be reminded of the product quality complaints (including AEs) hotline that has been established for all users of IQOS in Japan.

In the event that a medical event occurs in any of the study participant the study staff will be advised to call local emergency number to ensure appropriate medical treatment. The related cost for emergency treatment and transportation will be carried by the Sponsor. Adverse events that may occur during the study will not be collected.

13 ANALYSES AND REPORTING

13.1 Interim Analyses and Data Monitoring

This analysis may be conducted and reported in steps over time. Although these analyses will only be performed after database lock. Any interim reports will be incorporated into the final complete study report (Section 12.3).

13.2 Safety Reporting

Not applicable within this study.

13.3 Final Analyses

The final analysis will be performed after database lock and finalization of this SAP. A data review meeting will be held prior to database lock and analysis of the study data.

Any post-hoc, additional exploratory analyses completed to support planned study analyses, which were not identified in this SAP, will be documented and reported as applicable. Any unplanned analyses conducted prior to the finalization of the CSR will be clearly documented in the CSR, any additional analysis performed after the finalization of the CSR will either be included in an amendment of the CSR or be created as an addendum to the CSR.

14 POST-HOC ANALYSIS

This section describes additional analyses to be performed to further support the interpretation of the results from the study.

14.1 Additional Analysis to Explore Outcome of Primary Analysis

During the review of results from the primary analysis of the urinary biomarkers of exposure (BoExp) for both the Non-Exposure and Exposure Events it was identified that we could expand the predefined model to add more context and systematically evaluate the difference between the event types. The planned model, provided the estimates of the average levels of each BoExp during an exposure or Non-Exposure Event for each product use group, but did not compare between the events.

However for the indoor air quality compounds we defined the model to also compare across Exposure and Non-Exposure Events. When looking at the results and trying to understand the link between the indoor air quality compounds and the BoExp, we decided that it would be beneficial to have the similar comparison (across Exposure and Non-Exposure Events) for the BoExp. Since these values could be estimated by expanding the predefined model, it was decided to implement this change as a post hoc analysis.

To perform this analysis, an ‘estimate’ statement was added to the code to calculate the ratio of geometric means between the exposure and non-exposure group for each product use group. An example of the modified pseudo code from section 12.6.1.1 is presented below.

```
Proc mixed data=_data_ method=reml;
Class event_type sex product_use;
Model endpoint = baseline sex event_type product_use event_type*product_use
duration <IAQ covariates> / ddfm=kr;
estimate 'Cigarette Smoker' intercept 1 baseline xx sex .5 .5 product_use 1 0 0
event_type 1 event_type*product_use 1 0 0 0 0 duration xx IAQ1 xx ... IAQn xx /
alpha=0.05 cl;
estimate 'Cigarette Smoker Exp vs Non-exp' intercept 0 baseline yy sex 0 0
product_use 0 0 0 event_type 0 0 event_type*product_use 1 0 0 -1 0 0 duration
yy IAQ1 yy ... IAQn yy / alpha=0.05 cl;
Run;
```

Note that yy is the change in a covariate between the exposure vs the non-exposure groups. For example, the value for the covariate baseline is the change for baseline values in the exposure group minus baseline values in the non-exposure group for a product use group.

All estimates and respective 95% confidence intervals will be exponentiated and back-transformed to the original scale. This additional analysis will be presented and integrated with Table 15.2.2.1.1.

14.2 Additional Analysis to Explore Effect of Heatstick Consumption, Alcoholic Beverages and Food Consumption on Concentrations of HPHCs in Air

During the internal review period of the End of Trial Report for study P1-PES-01-JP and following a request of [REDACTED] after presentation of the preliminary results to the [REDACTED] it was identified that we should further examine the source of the increases of concentrations of Harmful or Potentially Harmful Constituents (HPHCs) in indoor air during a restaurant setting where the Non-Exposure and Exposure events took place by looking at the relationship between HeatStick consumption and its impact on HPHC concentrations including the IAQ markers acetaldehyde, formaldehyde, crotonaldehyde and acrolein. The statistical analysis defined in SAP version 1 did not allow an interpretation of these results directly, as it only included descriptive statistics.

To further explore the impact of potential impact of other covariates that may affect the concentrations of these HPHCs in air, we will use a linear regression model to assess the effects of beverage and food consumption on acetaldehyde, acrolein, crotonaldehyde and formaldehyde in addition to Heatsticks consumption. For acetaldehyde, we use a mixed effects repeated measures model representation to model the cumulative effects of these covariates over time as the covariates were measured on an hourly basis. A summary of the covariates used in the models are listed in Table 6.

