**Table 6. Covariates for Analysis of HPHCs in air**

Model	Time Points Used	Endpoint	Covariates
1	Average	Acetaldehyde	Baseline, Event Type, Cumulative Heatstick Consumption at 3 rd Hour
1	Average	Acrolein	Baseline, Event Type, Cumulative Heatstick Consumption at 3 rd Hour
1	Average	Crotonaldehyde	Baseline, Event Type, Cumulative Heatstick Consumption at 3 rd Hour
1	Average	Formaldehyde	Baseline, Event Type, Cumulative Heatstick Consumption at 3 rd Hour
2	All timepoints	Acetaldehyde	Baseline, Event Type, Heatstick Consumption, Alcoholic Beverages Consumption, Heatstick and Alcoholic Beverages interaction
3	Average	Acrolein	Baseline, Event Type, Cumulative Food Consumption during event
3	Average	Crotonaldehyde	Baseline, Event Type, Cumulative Food Consumption during event

Model 1 in Table 6 above describes a basic model relating the average levels of carbonyls to HeatSticks consumption. In this model the dependent variable is the change from baseline of the average reading of the carbonyls. Note that the average reading is taken as the mean of all readings from the three suitcases that were used to collect the carbonyls data. Baseline is the mean reading of all pre-event readings that were taken during a specific event. The endpoint change from baseline will be log-transformed prior to analysis. Baseline, Event type (Exposure or Non-Exposure), cumulative Heatstick usage will be fitted as fixed effects. Estimates of the carbonyl readings at mean levels of the covariates will be calculated for each event type. The estimates will be exponentiated and presented on the original scale. In addition to the estimates at an event level, the relative change in the carbonyls between an Exposure and Non-Exposure Event will be estimated as well. These estimates also be exponentiated and presented as a ratio of geometric means of an Exposure Event relative to a Non-Exposure Event. An example of the SAS code for model 1 is as given below.

```
proc mixed data=data;
class event exposure;
model ch=baseline exposure cumu_heatsticks /ddfm=kr solution;
estimate 'Non-exp 3rd hr' intercept 1 baseline xx exposure 1 0 cumu_heatsticks 0
/e cl alpha=.05;
```

```
estimate 'Exp 3hr hr' intercept 1 baseline yy exposure 0 1 cumu_heatsticks yy/e
cl alpha=.05;
estimate 'Change in carbonyl 3hr hr' intercept 0 baseline xy exposure 1 -1
cumu_heatsticks xy /e cl alpha=.05;
run;
```

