14.5 Additional Analysis to Explore Effect of Heatstick Consumption on Urinary BoExp

14.5.1 Effect of HeatStick Consumptions on Urinary BoExp in Compliant Exposure Set

During the review of the Clinical Study Report questions were raised about the relationship between HeatStick consumption and the levels of BoExp in the Compliant Exposure Set. A prior post-hoc analysis (14.2) investigated the effect of HeatSticks consumption and other covariates such as food consumption and consumption of alcoholic beverages on carbonyls in air. To corroborate the results from that analysis and impact of HeatSticks on the urinary BoExp, we will use the models developed for the BoExp (12.6.1.1, 12.6.2.2) and include a covariate for total HeatSticks consumption used during an Event. As with the existing models for the BoExp, the estimates for each product use group will be exponentiated and reported as geometric means and the ratio of geometric lsmeans between Exposure and Non-Exposure Events will be calculated and reported together with its 95% confidence intervals.

A sample of the code is presented below,

```
Proc mixed data=_data_ method=reml;
Class event_type sex product_use;
Model endpoint = baseline sex event_type product_use event_type*product_use
duration cumulative_heatsticks product_use*cumulative_heatsticks<IAQ covariates>
/ ddfm=kr;
estimate 'Cigarette Smoker Exposure event' intercept 1 baseline xx sex .5 .5
product_use 1 0 0 event_type 1 event_type*product_use 1 0 0 0 0 0 duration xx
cumulative_heatsticks xx IAQ1 xx ... IAQn xx / alpha=0.05 cl;
estimate 'Cigarette Smoker Non-Exposure event' intercept 1 baseline yy sex .5 .5
product_use 1 0 0 event_type 0 event_type*product_use 0 0 0 1 0 0 duration yy
cumulative_heatsticks 0 IAQ1 yy ... IAQn yy / alpha=0.05 cl;
estimate 'Cigarette Smoker Exposure vs Non-Exposure event' intercept 0 baseline
xx-yy sex 0 0 product_use 0 0 0 event_type 0 event_type*product_use 1 0 0 -1 0 0
duration xx-yy cumulative_heatsticks xx IAQ1 xx-yy ... IAQn xx-yy / alpha=0.05 cl;
Run;
```

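### The printed Exposure versus Non-Exposure contrasts for urinary biomarkers (SAP 14.1 and 14.5.1) zero out event type, so they are not estimable and cannot give the promised ratio

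*SAP*

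**What the plan says.** SAP 14.1 explains that the planned model gave biomarker levels per product use group and event type but did not compare the event types. It therefore adds an ESTIMATE statement "to calculate the ratio of geometric means between the exposure and non-exposure group for each product use group". The model has event_type, sex and product_use as CLASS effects and includes event_type, product_use and their interaction. The Cigarette Smoker contrast is printed as "product_use 0 0 0 event_type 0 0 event_type*product_use 1 0 0 -1 0 0 duration". On reporting: "This additional analysis will be presented and integrated with Table 15.2.2.1.1". That table is the analysis of the primary urinary biomarkers.

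SAP 14.5.1 extends the model with HeatStick consumption and states that "the ratio of geometric lsmeans between Exposure and Non-Exposure Events will be calculated and reported together with its 95% confidence intervals". Its MODEL statement includes "duration cumulative_heatsticks product_use*cumulative_heatsticks<IAQ covariates>". The Non-Exposure estimate is printed with "product_use 1 0 0 event_type 0 event_type*product_use 0 0 0 1 0 0 duration yy" and the comparison with "xx-yy sex 0 0 product_use 0 0 0 event_type 0 event_type*product_use 1 0 0 -1 0 0". None of its three ESTIMATE lines gives coefficients for the product use by HeatStick interaction.

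SAP 14.2 (Models 1 and 2, carbonyls in air) also compares event types. In Model 1 the first line is "estimate 'Non-exp 3rd hr' intercept 1 baseline xx exposure 1 0 cumu_heatsticks 0" and the second, for Exposure, uses `exposure 0 1`. The comparison uses `exposure 1 -1`. The text promises Exposure relative to Non-Exposure and describes xy as the average difference between Exposure and Non-Exposure.

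**The concern.** When a model holds a main effect and an interaction containing it, a difference between event types within one product use group is the event-type difference plus the interaction difference. The printed urinary contrasts keep the second part and set the first to zero. Such a combination of parameters has no unique value, so it has no valid estimate or confidence interval.

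The printed line is the only coefficient specification of the between-event ratio that goes into the primary biomarker table. SAP section 3 makes comparison of Non-Smokers with background part of the study's purpose. Anyone reproducing the ratio from the SAP would start from a contrast that cannot be estimated. If the executed program departed from the printed code, that departure needs to be on record.

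The fault in 14.2 is of another kind. Those lines are estimable, so the software raises no flag, but the sign of the comparison conflicts with the two lines above it.

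**Working it through.** **Inputs.** Event type has two levels and Exposure sorts first (SAP Table 5). The Compliant Exposure Set has three product use groups (SAP 12.6.1.2), giving six interaction cells. There are four Exposure and two Non-Exposure Events (SAP 12.6.2.1.1). There are 169 participants per event type, split 50/25/25% (SAP Table 1), taken as 85/42/42, so 338 rows.

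**The right contrast, by subtraction.** For Cigarette Smokers:

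| Term | Exposure line | Non-Exposure line | Difference |
|---|---|---|---|
| intercept | 1 | 1 | 0 |
| product_use | 1 0 0 | 1 0 0 | 0 0 0 |
| event_type | 1 0 | 0 1 | **1 -1** |
| interaction | 1 0 0 0 0 0 | 0 0 0 1 0 0 | 1 0 0 -1 0 0 |

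SAP 14.1 prints the last row correctly but has `0 0` for event_type.

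**Estimability, algebraically.** The event_type(Exposure) column equals the sum of its three interaction columns. A vector with +1 on event_type(Exposure) and -1 on those three cells is therefore a null vector of the design, and an estimable contrast must give 0 against it.

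- 14.1 as printed: 0 - 1 = -1. Not estimable.
- With `event_type 1 -1`: 1 - 1 = 0. The matching Non-Exposure check is -1 + 1 = 0. Estimable.
- 14.5.1 comparison as printed: 0 - 1 = -1. Not estimable.
- 14.5.1 Non-Exposure line as printed, against the matching Non-Exposure vector: 0 - 1 = -1. Not estimable. With `event_type 0 1`: 1 - 1 = 0.

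This does not depend on sample size, data or the air-quality covariates retained. The 14.5.1 lines also disagree among themselves: line 1 minus line 2 leaves event_type at 1, while line 3 prints 0.

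**Rank check, 14.1.** Columns: intercept 1 + baseline 1 + sex 2 + event_type 2 + product_use 3 + interaction 6 + duration 1 + one air-quality term 1 = 17. Rank: 6 cells + 1 (sex) + 3 continuous terms = 10. Appending the printed contrast gives 11 for all three groups; the corrected contrast gives 10. The Exposure line of 12.6.1.1 also gives 10.

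**Rank check, 14.5.1.** Adding cumulative HeatSticks (1 column) and its interaction with product use (3 columns) gives 21 columns and rank 10 + 3 = 13. The printed Non-Exposure line and the printed comparison each give 14 for every group, however the missing HeatStick interaction coefficients are read. With event_type corrected:

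| Interaction coefficients read as | Main minus sum | Exposure line and comparison |
|---|---|---|
| all 0 | xx - 0 = xx | not estimable (rank 14) |
| xx/3 in each column | xx - 3(xx/3) = 0 | estimable, but with the slope averaged over groups |
| xx in the group's own column | xx - xx = 0 | estimable, with the group's own slope |

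Under the last reading all three lines are estimable and line 1 minus line 2 equals line 3.

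**What the printed 14.1 contrast would return if estimability were ignored.** Assume true log ratios of 0.30 (Cigarette Smokers), 0.10 (IQOS Passive Users) and 0.05 (Non-Smokers); these are not trial values. Covariate coefficients are set to 0. For Cigarette Smokers, setting the last level to zero gives 0.30 - 0.05 = 0.25, which is the difference from the Non-Smoker effect. The minimum-norm solution gives 0.1875. The corrected contrast gives 0.30 (ratio 1.35) under both.

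**Sign in 14.2, Model 1.** Let d be the adjusted Exposure minus Non-Exposure effect and C the covariate part of that difference. Line 2 minus line 1 is d + C. With Non-Exposure as the first level, `exposure 1 -1` contributes -d.

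- xy read as Exposure minus Non-Exposure: the contrast is -d + C, an error of -2d. For |d| from 0.1 to 0.4 (assumed range), that is a factor of exp(0.2) = 1.22 to exp(0.8) = 2.23.
- xy read as Non-Exposure minus Exposure: the contrast is -(d + C), the reciprocal of the promised ratio.

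**The case against.** The SAP presents these blocks as examples, and the prose in 14.1 states the target clearly. PROC MIXED should flag a non-estimable row rather than print a ratio, so a programmer following the text literally would notice and correct it. A wrong number is therefore unlikely to have entered the primary table unseen through this fault. The analysis is post hoc, and the estimates serving the stated primary objective (SAP 6.1, 12.6.1.1) are sound. All of this stands, and it limits the point to a defective specification; it does not show a wrong result. It does not make the printed contrast usable, and no other coefficients are given.

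On 14.5.1, reading the missing HeatStick coefficients as zero is probably not what the software would do, since it fills in unlisted higher-order terms. What remains then is the averaged slope. The prose there mentions only a HeatStick covariate and no interaction, so dropping the term would be another way to reconcile text and code.

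On 14.2, the ESTIMATE lines ask for their coefficients to be printed, and a careful reader comparing the three lines could spot the sign. That helps detection, but the lines still contradict one another.

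SAP 14.4 reports that an incorrect specification of the carbonyl air model did not converge and that the CRO's results then differed from the plan. It concerns another model and was documented. It shows only that a specification fault has had consequences in this study.

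**Conclusion.** The concern holds. As printed, the between-event contrasts in 14.1 and 14.5.1 and the Non-Exposure line in 14.5.1 are not estimable for any product use group. This is algebra under the printed CLASS and MODEL statements and rests on no assumed effect size. In 14.5.1, correcting event_type alone does not settle the matter, because the HeatStick interaction coefficients are also missing. The 14.2 comparison contradicts its own companion lines in sign. The size of that error depends on the true effect and on how xy is read, so the factor of 1.22 to 2.23 is illustrative.

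The planned estimates in 12.6.1.1 are unaffected. The documents do not show which program was run, so this is no evidence that reported ratios are wrong. It should be fixed because the ratio sits in the primary biomarker table and addresses a stated purpose of the study.

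**What to change.** 1. **14.1:** code `event_type 1 -1` with `event_type*product_use 1 0 0 -1 0 0` for Cigarette Smokers, and interaction vectors `0 1 0 0 -1 0` and `0 0 1 0 0 -1` for the other two groups.
2. **14.5.1:** code `event_type 0 1` in the Non-Exposure line and `event_type 1 -1` in the comparison. For the product use by HeatStick interaction, put xx in the group's own column in the Exposure and comparison lines and 0 in the Non-Exposure line. If the interaction was not intended, remove it from the MODEL statement so that code and prose agree.
3. **14.2, Models 1 and 2:** with the level order of the first two lines, use `exposure -1 1` and define xy explicitly as Exposure minus Non-Exposure. If the true level order is the reverse, correct the first two lines instead.
4. **Executed program:** compare it with the printed code. If it matched, correct it, rerun it, and document the change in the study report as SAP sections 3 and 13.3 provide. If it already differed, document that.

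The cost is a few coefficients, one program check and possibly one rerun. No new data are needed.

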**Table 6. Covariates for Analysis of HPHCs in air**

Model	Time Points Used	Endpoint	Covariates
1	Average	Acetaldehyde	Baseline, Event Type, Cumulative Heatstick Consumption at 3 rd Hour
1	Average	Acrolein	Baseline, Event Type, Cumulative Heatstick Consumption at 3 rd Hour
1	Average	Crotonaldehyde	Baseline, Event Type, Cumulative Heatstick Consumption at 3 rd Hour
1	Average	Formaldehyde	Baseline, Event Type, Cumulative Heatstick Consumption at 3 rd Hour
2	All timepoints	Acetaldehyde	Baseline, Event Type, Heatstick Consumption, Alcoholic Beverages Consumption, Heatstick and Alcoholic Beverages interaction
3	Average	Acrolein	Baseline, Event Type, Cumulative Food Consumption during event
3	Average	Crotonaldehyde	Baseline, Event Type, Cumulative Food Consumption during event

Model 1 in Table 6 above describes a basic model relating the average levels of carbonyls to HeatSticks consumption. In this model the dependent variable is the change from baseline of the average reading of the carbonyls. Note that the average reading is taken as the mean of all readings from the three suitcases that were used to collect the carbonyls data. Baseline is the mean reading of all pre-event readings that were taken during a specific event. The endpoint change from baseline will be log-transformed prior to analysis. Baseline, Event type (Exposure or Non-Exposure), cumulative Heatstick usage will be fitted as fixed effects. Estimates of the carbonyl readings at mean levels of the covariates will be calculated for each event type. The estimates will be exponentiated and presented on the original scale. In addition to the estimates at an event level, the relative change in the carbonyls between an Exposure and Non-Exposure Event will be estimated as well. These estimates also be exponentiated and presented as a ratio of geometric means of an Exposure Event relative to a Non-Exposure Event. An example of the SAS code for model 1 is as given below.

```
proc mixed data=data;
class event exposure;
model ch=baseline exposure cumu_heatsticks /ddfm=kr solution;
estimate 'Non-exp 3rd hr' intercept 1 baseline xx exposure 1 0 cumu_heatsticks 0
/e cl alpha=.05;
```

```
estimate 'Exp 3hr hr' intercept 1 baseline yy exposure 0 1 cumu_heatsticks yy/e
cl alpha=.05;
estimate 'Change in carbonyl 3hr hr' intercept 0 baseline xy exposure 1 -1
cumu_heatsticks xy /e cl alpha=.05;
run;
```

Note that xx is the average of the observations of the associated covariate in the Non-Exposure Event and yy is the average of the observations of the associated covariates in the Exposure Event. The value for the covariates to estimate the relative change between events denoted by xy is the average difference between Exposure and Non-Exposure events.

For acetaldehyde in Model 2, all 3 timepoints will be used in the analysis and a repeated measures analysis will be used to model the effects over time. Due to the equally spaced observations, a toeplitz structure will be fitted to the covariance structure to allow for variance components to be estimated at each timepoint. Heatstick and alcohol consumption will be fitted as fixed effects and their interaction terms will be added to the model as well.

```
proc mixed data=data;
class event exposure time;
model change=baseline exposure cumu_alcohol cumu_heatsticks
cumu_alcohol*cumu_heatsticks /ddf=kr solution;
repeated time/type=toep subject=event;
estimate 'Non-exp 3rd hr' intercept 1 baseline xx exposure 1 0 cumu_alcohol xx
cumu_heatsticks 0 cumu_alcohol*cumu_heatsticks 0 /e cl alpha=.05;
estimate 'Exp 3hr hr' intercept 1 baseline yy exposure 0 1 cumu_alcohol yy
cumu heatsticks yy cumu alcohol*cumu heatsticks yy/e cl alpha=.05;
estimate 'Change in carbonyl 3hr hr' intercept 0 baseline xy exposure 1 -1
cumu_alcohol xy cumu_heatsticks xy cumu_alcohol*cumu_heatsticks xy/e cl
alpha=.05;
run;
```

Note that xx is the average of the observations of the associated covariate in the Non-Exposure Event and yy is the average of the observations of the associated covariates in the Exposure Event. The value for the covariates to estimate the relative change between event types denoted by xy is the average difference between Exposure and Non-Exposure events.

Model 3 will be similar to Model 1 but with cumulative Heatstick consumption replaced by cumulative food consumption. The estimates from this model will be calculated at the mean levels calculated for each event type.

Due to the irregular nominal times of the carbonyls, food/beverages and HeatStick consumption collection as shown in Table 7, we will pro-rate the values of the covariates against the time of carbonyl collection. For example, during a Non-Exposure Event at the end of the 1st hour for the carbonyls taken at 1730 the corresponding value for food or alcoholic beverages will be the sum of the 1st hour plus half of the 2nd hour. Similarly for an Exposure event, for the 2nd hour carbonyl reading the corresponding observation for food/beverages will be the cumulative sum until 2.5 hours and Heatsticks consumption will be the sum up to the 2nd hour plus a quarter of the 3rd hour observation.

From this model we will estimate the cumulative effects of the covariates on carbonyls at the end of 3 hours and also estimate the average concentrations of carbonyls in air over 3 hours.

For each type of carbonyl, boxplots of observations at each timepoint will be plotted against time and grouped by Event in the same figure.

A sensitivity analysis will also be performed matching the endpoints by the nominal timepoints, this approach is more conservative as the cumulative effects of food/beverage or HeatStick consumption is lower than what it actually was during time of the carbonyls reading.

Table 7. Nominal Sampling Times of Food/Beverages, IAQ parameters (Carbonyls) and HeatSticks consumption during Exposure and Non-Exposure Events

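### SAP 14.2 example code: the change row has the opposite event-type sign to the two event-level rows, so the three estimates cannot all be what the text says

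*SAP*

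**What the plan says.** SAP 14.2 fits three post-hoc models to carbonyls in indoor air. Model 1 has baseline, event type (the class variable `exposure`) and cumulative HeatSticks as fixed effects. Three ESTIMATE rows follow:

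- Non-Exposure mean: "estimate 'Non-exp 3rd hr' intercept 1 baseline xx exposure 1 0 cumu_heatsticks 0"
- Exposure mean: "estimate 'Exp 3hr hr' intercept 1 baseline yy exposure 0 1 cumu_heatsticks yy/e"
- Change: "estimate 'Change in carbonyl 3hr hr' intercept 0 baseline xy exposure 1 -1"

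The text defines xx as a covariate's average in Non-Exposure Events and yy as its average in Exposure Events. The value xy used in the change row is "denoted by xy is the average difference between Exposure and Non-Exposure events". All three estimates are exponentiated, and the change is "presented as a ratio of geometric means of an Exposure Event relative to a Non-Exposure Event".

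The Model 2 code (acetaldehyde, all time points) uses the same three patterns for `exposure`. No code is printed for Model 3, but "Model 3 will be similar to Model 1 but with cumulative Heatstick consumption replaced by cumulative food consumption".

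On the outcome, 14.2 says: "The endpoint change from baseline will be log-transformed prior to analysis". Section 14.6 uses the same wording for its change from the pre-event average.

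**The concern.** The two event-level rows put Non-Exposure on the first level of `exposure` and Exposure on the second. On that coding `exposure 1 -1` is Non-Exposure minus Exposure, the reverse of the direction in the text. If Exposure is in fact the first level, the change row points the right way but each event-level row picks up the other event type's coefficient.

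Section 14.2 was added to look for the source of the rises in indoor-air constituents. Followed as printed, its code would mislabel either the ratio or both means, and the ratio could fall on the wrong side of 1. The software would give no warning, because `exposure 1 -1` with a zero intercept is a valid, estimable contrast.

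**Working it through.** **Inputs.** The coefficients come from the SAP 14.2 code for Model 1. HS is the average cumulative HeatStick count in Exposure Events; it is 0 in Non-Exposure Events. The plan gives no numerical result to reproduce.

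**Step 1: subtract the rows.**

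| Row | Intercept | Baseline | Level 1 | Level 2 | HeatSticks |
|---|---|---|---|---|---|
| Non-Exposure | 1 | xx | 1 | 0 | 0 |
| Exposure | 1 | yy | 0 | 1 | HS |
| Exposure minus Non-Exposure | 0 | yy − xx | −1 | 1 | HS |
| Change row as printed, xy = Exposure minus Non-Exposure | 0 | yy − xx | 1 | −1 | HS |

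The last two lines differ by (0, 0, 2, −2, 0): twice the event-type effect on the log scale, hence a factor of R² or 1/R² after exponentiation. In Model 2 the alcohol and interaction terms add further covariate differences but leave the `exposure` coefficients the same.

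**Step 2: try every reading.** Let R be the fitted event-type ratio (Exposure/Non-Exposure) adjusted for the other covariates, H the part of the ratio due to covariate differences, and T = R × H the correct total ratio.

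| Sign of xy | First level | Change row gives | Quotient of the two means gives |
|---|---|---|---|
| Exposure minus Non-Exposure | Non-Exposure | T/R² | T |
| Exposure minus Non-Exposure | Exposure | T | T/R² |
| Reversed | Non-Exposure | 1/T | T |
| Reversed | Exposure | R²/T | T/R² |

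A consistent set would show T in both of the last two columns. No line does so in general. In the second and fourth lines the Non-Exposure mean is multiplied by R and the Exposure mean divided by R. In the first line the change row mixes directions, so inverting the output does not repair it.

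**Step 3: size, for assumed R, with xy as Exposure minus Non-Exposure.**

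| R | R² (discrepancy factor) | Ratio reported if Non-Exposure is first and H = 1 (T/R² = 1/R) | Correct ratio |
|---|---|---|---|
| 0.8 | 0.64 | 1.25 | 0.80 |
| 1.0 | 1.00 | 1.00 | 1.00 |
| 1.2 | 1.44 | 0.83 | 1.20 |
| 1.5 | 2.25 | 0.67 | 1.50 |
| 2.0 | 4.00 | 0.50 | 2.00 |

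With H = 1.3 and R = 1.5, T = 1.95 and the reported ratio is 1.95/2.25 = 0.87. With xy reversed and Non-Exposure first, the result is 1/T even at R = 1: for H = 1.3, 1/1.3 = 0.77 instead of 1.30.

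**Step 4: worked example (assumed values).** Intercept 1, baseline slope 0.2, event-type effect 0.4, HeatStick slope 0.002, xx = 1.0, yy = 1.1, HS = 100.

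- Correct Non-Exposure mean: exp(1 + 0.2) = 3.320.
- Correct Exposure mean: exp(1 + 0.22 + 0.4 + 0.2) = 6.172.
- Correct ratio: exp(0.02 + 0.4 + 0.2) = 1.859.
- Non-Exposure first: means right; change row exp(0.02 − 0.4 + 0.2) = 0.835.
- Exposure first: change row 1.859, but the means come out as exp(1 + 0.2 + 0.4) = 4.953 and exp(1 + 0.22 + 0.2) = 4.137, with quotient 0.835.
- Non-Exposure first with xy reversed: exp(−0.02 − 0.4 − 0.2) = 0.538 = 1/1.859.

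**Step 5: can the SAP settle the order?** No. The 14.2 event-level rows imply Non-Exposure first. The code in 14.1 and 14.5.1 puts Exposure first for the corresponding variable `event_type`. For the sign of xy, 14.1 defines its own covariate difference as "the change for baseline values in the exposure group minus baseline values in the non-exposure group", which supports Exposure minus Non-Exposure, but 14.2 does not say so.

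**Secondary point: the outcome.** The logarithm of a change is undefined when the change is zero or negative. SAP section 8 writes geometric relative change as a difference of logs, and 12.6.2.1.4 logs the air values other than particulate matter, so ln(event) − ln(pre-event) was probably meant. For particulate matter, 14.6 repeats the 12.6.2.1.3 model with a logged change, whereas 12.6.2.1.4 leaves those values unlogged.

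**The case against.** The code is offered as an example, and the Model 2 block has another slip (`ddf` for `ddfm`), so it may never have been run literally. The prose states the intended ratio clearly. The analysis is post hoc. Carbonyl ratios between event types also come from the LSMEANS differences in 12.6.2.1.1 and 14.6, which do not use this row. The reversed reading of xy is the less natural one. The size is hypothetical: R in Models 1 and 2 is taken at equal HeatSticks and may be near 1 if HeatSticks explain the difference. Model 3 has no printed code. The outcome wording is a separate matter, and 14.6, as a later addition, may set its own transformation.

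Most of this limits the weight of the point without removing it. Clear prose shows that the printed coefficients are wrong; it does not make them right. The LSMEANS models do not adjust for HeatSticks, alcohol or food, so they do not replace 14.2. Nor is R near 1 a safe assumption. Section 12.6.2.1.1 numbers six events, and Model 1 averages readings within an event, leaving about six observations for four fixed-effect parameters. Since Non-Exposure Events have no HeatSticks, R is an extrapolation from very few points. In Model 3, which has no HeatStick term, R absorbs any HeatStick effect that food does not explain. It stands that the effect on reported results is unknown and that the reversed-xy cases are secondary.

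**Conclusion.** The inconsistency is certain: it follows from the coefficients alone and needs no assumed effect size. Which row is wrong cannot be settled from the documents. On the natural reading of xy the discrepancy is a factor of R² and vanishes only at R = 1; on the reversed reading R = 1 alone is not enough. The numerical sizes rest on assumed R and H.

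The contrast error reaches Models 1 and 2 of 14.2, and Model 3 if it copies Model 1. The primary urinary analysis, the planned indoor-air models, the HeatStick slope and the 14.6 LSMEANS contrasts are not affected by it. It should be corrected, but it does not touch the study's main conclusions. The wording of the logged change is a lesser point to clear up at the same time.

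**What to change.** - State the level order of `exposure` and define xy as Exposure minus Non-Exposure for Models 1, 2 and 3.
- With Non-Exposure first, write the change row as `exposure -1 1`. With Exposure first, keep `1 -1` and swap the `exposure` coefficients in the two event-level rows.
- Add a check that each reported ratio equals the quotient of the two event-level geometric means.
- Look at the existing output first: the rows request the `/e` option, which prints the coefficients used, so it may show whether a rerun is needed. Rerun 14.2 only if the code was used as printed.
- In 14.2 and 14.6, define the outcome as ln(event value) − ln(pre-event mean), and reconcile 14.6 with 12.6.2.1.4 for particulate matter.

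The cost is a few coefficients and a couple of sentences in the SAP, plus a conditional rerun of small post-hoc models.
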